9.5 STUDY ASSESSMENTS

9.5.1 Screening and Baseline Assessments

Treatment may occur on the day of the Screening Visit (Visit 1) or any following day up to 1 week (Baseline and Drug Administration, Visit 1a). If drug administration occurs on same day as screening then all assessments in Visit 1 and Visit 1a listed in Schedule of Assessments ([Table 4](#)) will be combined.

9.5.1.1 Demographics

Subject demographic information will be collected at the Screening Visit. Demographic information includes date of birth (or age), sex, race, and ethnicity.

9.5.1.2 Medical History

Medical and surgical history and current medical conditions will be recorded at the Screening Visit. All relevant medical and surgical history must be recorded in the

CRF, including any record or history of cystoscopy and the diagnosis of IC/BPS.

9.5.1.3 Medication History

All relevant medication history must be recorded in the CRF.

9.5.1.4 Physical and Pelvic Examination

A comprehensive physical examination will be performed at the Screening Visit (V1). The physical examination will include evaluations of the following: general appearance; eyes, ears, nose, and throat; chest (including heart and lungs); abdomen (palpation and gastrointestinal sounds), extremities; and skin. Weight and height will also be measured and will be recorded in the CRF. A pelvic examination will also be conducted which may be performed without speculum. Results from a pelvic examination performed within 7 days prior to the Screening Visit (V1) may replace a V1 pelvic examination. Documentation of the physical and pelvic examination results will be included in the source documentation. Significant findings at the Screening Visit will be recorded in the CRF.

9.5.1.5 Urine Screening Tests

A 30-mL urine sample will be collected and analyzed for pregnancy in women of childbearing potential, drug screen, and for standard urine analysis testing.

The urine sample will be analyzed for hematuria by dipstick urinalysis. If the urine dipstick is positive for blood, the investigator will evaluate the subject further before proceeding, (such as assessing the subject's history to determine if the subject is menstruating, or performing a full urinalysis and if appropriate, a urine culture, to determine if the subject has a kidney or urinary tract infection, or cystoscopy prior to enrollment). If the investigator determines that active bleeding is not occurring and that it is safe for the subject, the subject may continue in the study.

9.5.1.6 Catheter Tolerance

All subjects will be catheterized with the hydrophilic ColoplastSpeediCath 8 Fr and 12 Fr, respectively (for females and males). Each subject will be assessed for the ability to tolerate the catheter after randomization into the study, based on the

investigator's judgment.

9.5.1.7 [REDACTED]

9.5.1.8 Pelvic Pain and Urgency/Frequency (PUF) Questionnaire

Subjects will be asked to fill out the Pelvic Pain and Urgency/Frequency (PUF) Questionnaire, and it will be scored by the investigator. Subjects must have a score of ≥ 15 and < 30 on the PUF questionnaire to qualify for the study.

9.5.1.9 Bladder Pain and Urgency 11-Point Numerical Rating Scales (NRS)

As part of screening, subjects will be asked to fill out two sets of the 11-point bladder pain NRS and the 11-point urgency NRS, one at screening and one 15 minutes (± 5 minutes) after voiding just prior to study drug administration. There is no minimum score requirement for the urgency NRS scales for patients to enter the study. For the Pain NRS, both the screening and [REDACTED] pain NRS requires a score of ≥ 5.0 to enter the trial and receive study drug.

9.5.1.10 Safety Assessments

Safety will be assessed by clinical laboratory tests (hematology, clinical chemistry, and urinalysis), vital signs measurements, and AE reporting.

9.5.1.10.1 Clinical Laboratory Testing

The local laboratory will be used for all laboratory testing required during the study

except for baseline and 1-hour plasma lidocaine, which will be analyzed by the central laboratory. Reports from the laboratory should be filed with the source documents for each subject. Samples will be obtained at the visits designated in **Table 4**. Additional samples may be collected for further evaluation of safety as warranted by the investigator's discretion. The clinical laboratory tests performed during the study are provided in **Table 2**. However, with the exception of qualifying results for hematuria, drugs of abuse and pregnancy, no other clinical laboratory results are required prior to randomization.

Table 2. Clinical Laboratory Tests

Hematology: Complete blood count (CBC): As defined by local laboratory	Serum Chemistry: Alanine transaminase (ALT) Alkaline phosphatase (ALP) Aspartate transaminase (AST) Blood urea nitrogen (BUN) Calcium Creatinine γ -glutamyltransferase (GGT) Glucose Lactate dehydrogenase (LDH) Potassium Protein, total Sodium
Dipstick Urinalysis: Color pH Specific gravity Blood/hemoglobin Leukocyte esterase Ketones Protein	
Additional Tests: Urine β -hCG for women of childbearing potential Urine drug screen INR and activated partial thromboplastin time Clean catch urine for bacterial culture if the urinalysis indicates: Plasma for lidocaine concentration	

β -hCG = beta human chorionic gonadotropin;

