Lidocaine is a well-characterized small molecule drug used for local anesthesia. The uncharged form of lidocaine is able to traverse membranes and enter into systemic circulation. AEs are primarily dose-related upon reaching a 6- $\mu\text{g}/\text{mL}$ serum lidocaine concentration. The maximum recommended intravenous dose for adults is 300 mg, which is well above the 200 mg lidocaine dose in URG101. Additionally, intravenous lidocaine is also a class I antiarrhythmic and is often used simultaneously with intravenous heparin in the acute care setting after myocardial infarction. Heparin (a large, naturally sulfated polysaccharide) is an intravenous anticoagulant used for the prophylaxis and treatment of arterial or venous thrombosis and coagulopathies. Heparin's large size prevents it from being absorbed across epithelial surfaces.

The previous human experience of intravesical buffered lidocaine-heparin in the URG101-101 study involved 43 subjects on active drug. The intravesical instillation of buffered lidocaine-heparin (160 mg lidocaine, 40,000 units heparin, pH 7.8) did not alter the prothrombin time (PT) and activated partial thromboplastin time (aPTT) of these subjects, consistent with the heparin component not entering systemic circulation. Monitoring of serum lidocaine concentrations at 1 hour demonstrated

that the serum lidocaine concentrations were < 1.0 $\mu\text{g}/\text{mL}$ for most subjects (32 of 43), with only 11 subjects with serum lidocaine concentrations > 1.0 $\mu\text{g}/\text{mL}$, and the highest concentration of 1.5 $\mu\text{g}/\text{mL}$. In the URG101-104 study serum levels of lidocaine ranged from 0.24 to 2.0 $\mu\text{g}/\text{mL}$, with an average of 0.51 $\mu\text{g}/\text{mL}$, and neither the aPTT nor the PT was altered in any subject²⁰. These serum lidocaine concentrations are well below the toxic 6- $\mu\text{g}/\text{mL}$ concentration for lidocaine and changes in bleeding parameters have not been seen; therefore, the lidocaine and heparin in URG101 do not pose an unacceptable safety risk.

In summary, buffered lidocaine-heparin provides relief of bladder pain and urgency over both short-term and medium-term time periods, for which there is no currently FDA-approved therapy, and thus may be beneficial for individuals with chronic pelvic pain of bladder origin.

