9.5.1.10.3 Adverse Events and Other Events of Interest

An AE is any untoward medical occurrence in a subject who is administered an investigational product. An AE does not necessarily have a causal relationship with the study drug.

The criteria for identifying AEs include the following:

- Any unfavorable and unintended sign (including an abnormal laboratory finding), symptom, or disease temporally associated with the use of an investigational product, whether or not considered related to the investigational product
- Any new disease or exacerbation of an existing disease
- Any deterioration in non-protocol-required measurements of a laboratory value or other clinical test (e.g., electrocardiogram [ECG] or x-ray) that results in symptoms, a change in treatment, or discontinuation of study drug
- Recurrence of an intermittent medical condition (e.g., headache) not present pretreatment (baseline)
- An abnormal laboratory test result should be considered an AE if the identified laboratory abnormality leads to any type of intervention, whether prescribed in the protocol or not, and after repeat confirmatory testing has been conducted

A laboratory result should be considered by the investigator to be an AE if it includes the following:

- Results in an intervention, based on medical evaluation (e.g., potassium supplement for hypokalemia)

- Results in any out of range laboratory value that in the investigator's judgment fulfills the definitions of an AE with regard to the subject's medical profile

All AEs observed during the study will be reported on the CRF. All AEs, regardless of relationship to study drug or procedure, should be collected beginning from the time the subject signs the ICF through the last visit. AEs reported prior to randomization will be termed medical history. SAEs will not be considered medical history and will be collected for 72 hours after the last dose.

Abnormal laboratory values should not be listed as separate AEs if the values are considered to be part of the clinical syndrome that is being reported as an AE. Any laboratory abnormality considered to constitute an AE should be reported as an AE on the CRF.

It is the responsibility of the investigator to review all laboratory findings in all subjects and determine if they constitute an AE. Medical and scientific judgment should be exercised in deciding whether an isolated laboratory abnormality should be classified as an AE.

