9.5.3 Pharmacokinetic Assessments

9.5.3.1 Lidocaine Concentration

A blood sample will be collected to determine the concentration of lidocaine in the peripheral blood. An initial blood sample will be collected at baseline prior to study drug administration, and a second blood sample will be collected 1 hour (\pm 10 minutes) after administration of the study drug (i.e., 1 hour after instillation) to determine plasma lidocaine concentrations.

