9.6 DATA QUALITY ASSURANCE

9.6.1 Monitoring

The study will be monitored by designees of Urgen N.A., Inc. at all stages of study conduct, from inception to completion, in accordance with current GCP. This monitoring will be in the form of site visits and other communication and will include review of original source documents and CRFs. The monitor will notify the investigator prior to conducting any investigational site visit. The frequency of these visits will depend upon the progress of the study, and will include monitoring to assess facilities and equipment, recruiting, record-keeping, protocol adherence, data collection, AE reporting, and other factors.

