9.7.1.5 Definitions of Analysis Sets

The safety analysis set will include all subjects who receive at least one dose of study drug and have at least one post dose safety assessment.

The intent-to-treat set will include all randomized subjects who receive study drug.

The per protocol set will include all subjects who sufficiently comply with the protocol. Details of the evaluability criteria will be determined before database lock and treatment unblinding.

The pharmacokinetic (PK) set will include all subjects who receive at least one dose of study drug and have sufficient data to calculate PK parameters.

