10.3 MONITORING PROCEDURES

The sponsor's contract research organization or clinical research associate (CRA) will maintain contact with the investigator and designated staff by telephone, letter, or email between study visits. Monitoring visits to each site will be conducted by the assigned CRA as described in the monitoring plan. The investigator, or if regionally required, the head of the medical institution will allow the CRA to inspect the clinical, laboratory, and pharmacy facilities to assure compliance with GCP and local regulatory requirements. The CRFs and subject's corresponding original medical records (source documents) are to be fully available for review by the sponsor's

representatives at regular intervals. These reviews verify adherence to study protocol and data accuracy in accordance with local regulations. All records at the site are subject to inspection by the local auditing agency and IRB or IEC review.

In accordance with ICH E6, Section 1.52, source documents include, but are not limited to the following:

- Clinic, office, or hospital charts
- Copies or transcribed health care provider notes which have been certified for accuracy after production
- Recorded data from automated instruments such as IxRS, x-rays, and other imaging reports (e.g., sonograms, computed tomography scans, magnetic resonance images, radioactive images, ECGs, rhythm strips, polysomnographs, pulmonary function tests), regardless of how these images are stored, including microfiche and photographic negatives
- Pain, quality-of-life, or medical history questionnaires completed by subjects
- Records of telephone contacts
- Diaries or evaluation checklists
- Drug distribution and accountability logs maintained in pharmacies or by research personnel
- Laboratory results and other laboratory test outputs (e.g., urine pregnancy test result documentation and urine dip-sticks)
- Correspondence regarding a study subject's treatment between physicians or memoranda sent to the IRBs
- CRF components (e.g., questionnaires) that are completed directly by subjects and serve as their own source

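### On the protocol text, sites and monitors may see plasma lidocaine levels before database lock, and these largely separate the lidocaine-containing arms from placebo and heparin

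*Combined protocol and SAP*

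**What the plan says.** Section 9.5.1.10.1 gives all testing to the local laboratory except the lidocaine samples taken at baseline and at 1 hour, "which will be analyzed by the central laboratory. Reports from the laboratory should be filed with the source documents for each subject". Table 2 in that section includes "Plasma for lidocaine concentration" under additional tests. Section 9.5.3.1 takes a baseline sample, and then "a second blood sample will be collected 1 hour" after dosing, in every arm.

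Section 9.5.1.10.3 states: "It is the responsibility of the investigator to review all laboratory findings in all subjects and determine if they constitute an AE". Monitoring under section 9.6.1 runs through all stages of the study and "will include review of original source documents and CRFs". Section 10.3 counts "Laboratory results and other laboratory test outputs" among the source documents open to the sponsor's representatives.

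The only procedure for breaking the blind is the single-subject emergency request in section 9.5.6.4. On the per-protocol set, section 9.7.1.5 says: "Details of the evaluability criteria will be determined before database lock and treatment unblinding".

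**The concern.** The trial is double-blind, and section 9.2 relies on blinding to limit bias in collecting data and evaluating endpoints. A post-dose lidocaine level is a marker of treatment: it should be present after URG101 or lidocaine and near zero after placebo or heparin. If the report goes into the site file, blinded staff learn which of two treatment classes the subject belongs to.

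Three kinds of judgement could then be made with that knowledge:

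- the investigator's grading of adverse event severity and of causality (section 9.5.1.10.3 and Table 3);
- data queries and the follow-up questions on returned diaries (section 9.5.2.3);
- the evaluability decisions that section 9.7.1.5 places before unblinding.

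**Working it through.** The plan states no figure on this point, so there is none to reproduce. The check has two parts: where a lidocaine report would go, and what it would reveal.

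**Where the report goes**

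1. *Broad reading of the filing sentence.* It covers any laboratory's report, including the central laboratory named just before it. The lidocaine report then goes into the subject's source documents.
2. *Narrow reading.* It covers the local laboratory only. The filing sentence then does not reach lidocaine. But the review duty in 9.5.1.10.3 and the source-document list in 10.3 are not limited to local results, and Table 2 places lidocaine among the laboratory tests. The narrow reading removes one link and adds no restriction.
3. *Timing.* No turnaround time or release date is given. Adverse events go on the CRF, so a review that decides whether a finding is one belongs before lock. This is an inference, not a stated date.
4. *Withholding rule.* The documents provided contain no rule that masks, holds or delays the lidocaine result.

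**What the report reveals**

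Inputs:

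- allocation 2:1:2:1 for URG101:placebo:lidocaine:heparin, target 180, maximum 300 (synopsis, section 9.1);
- in study URG101-104, "serum levels of lidocaine ranged from 0.24 to 2.0" µg/mL, mean 0.51 (section 7.4), with 28 subjects enrolled (section 7.3);
- local anesthetic by any route within 24 hours before dosing is an exclusion (section 9.3.2).

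Size of the two classes:

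- With lidocaine: 180 × (2 + 2)/6 = 120. Without: 180 × (1 + 1)/6 = 60.
- At the maximum of 300: 200 and 100.

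Chance that a subject is on URG101, if every lidocaine-treated subject is detectable:

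- before the result: 2/6 = 1/3;
- after a positive result: 2/(2 + 2) = 1/2;
- after a negative result: 0.

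Allowing for undetectable levels. The assay limit is not given. Assume that it lies below 0.24 µg/mL, that all 28 earlier subjects were measured, and that lidocaine alone gives similar levels. With 0 of 28 undetectable, the exact one-sided 95% upper bound on the undetectable share m is 1 − 0.05^(1/28) = 0.101. Taking the non-lidocaine arms as negative:

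- correct class = 1 − (2/3) × m, which is 1.00 at m = 0 and 0.933 at m = 0.101;
- chance of no lidocaine given a negative result = (1/3)/[(1/3) + (2/3) × m], which is 1.00 at m = 0 and 0.832 at m = 0.101.

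Under these assumptions, 93% to 100% of subjects would be placed in the right class. Because URG101 and lidocaine alone both give a positive result, the level does not tell them apart.

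**The case against.** The strongest reply is that lidocaine is a pharmacokinetic measurement, not a safety test. Section 9.5.1.10 describes the safety laboratory tests as hematology, chemistry and urinalysis. Lidocaine has its own assessment section (9.5.3), endpoints (9.7.1.4) and analysis set (9.7.1.5). The main clause of the quoted passage is about the local laboratory. Drug preparation and emergency unblinding are deferred to a Study Procedures Manual, and a release rule could be there or in laboratory instructions. This stands as a limit: the text permits release to sites but does not clearly order it. It does not remove the point, because Table 2 and the unrestricted review duty point the other way.

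A reader might infer that the primary comparisons with placebo and heparin are unblinded. The documents do not support that. SPID-12 is rated by the subject within 12 hours, and nothing says that subjects receive the result. The comparison with lidocaine alone, which tests heparin's contribution, is not exposed by the level at all.

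A reader might also infer that class is revealed for every one of the 180 subjects. That needs an assay limit and levels for the other arms that the documents do not give.

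Two further routes of harm are weak. Site pooling depends on small enrolment and a pre-specified method (section 9.7.1.14). Effects on later subjects are speculative, since each receives one centrally randomized dose.

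The remaining exposure is also bounded. Per-protocol exclusion for missing scores already has numeric rules (section 9.7.2.2), the primary analysis is on the ITT set, and adverse events are summarized descriptively.

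**Conclusion.** The gap is real and should be closed. On the protocol text, a site, its monitor and sponsor representatives may read lidocaine levels before lock, and no visible rule prevents it. The levels would largely separate 120 lidocaine-treated subjects from 60 others at the planned size, with about 93% to 100% classified correctly under the stated assumptions.

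The consequence is limited to adverse event causality and severity, queries, and those per-protocol decisions not already fixed by numeric rules. The documents do not show a bias in the self-rated primary endpoint. The conclusion also rests on two things that cannot be checked here: how quickly results are returned, and whether a manual outside these documents already withholds them. If one does, the protocol text should be brought into line with it.

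**What to change.** In section 9.5.1.10.1, exempt baseline and 1-hour plasma lidocaine from the source-document filing rule. State that the central laboratory holds these results and releases them to site, monitoring and blinded sponsor staff only after database lock. In section 9.5.1.10.3, exempt them from routine investigator review.

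Leave emergency unblinding (9.5.6.4) as it is. Section 9.5.1.10.4 treats significant treatment-emergent laboratory abnormalities as events of interest, so the sponsor must reconcile the exemption with that reporting. No clinical rule is proposed here.

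The cost is a short protocol change and matching central laboratory instructions, with no added samples, visits or subjects. The downside is that sites do not see lidocaine levels before lock. Those levels are not required before randomization, and their only stated analysis is the pharmacokinetic one in section 9.7.1.16.

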9.5.1.10.2 Vital Signs

Vital sign measurements (i.e., systolic and diastolic blood pressure [mmHg], and pulse [beats per minute]) will be obtained at the visits designated on the schedule of assessments ([Table 4](#)). Blood pressure and pulse will be measured after the subject has been sitting for 3 to 5 minutes. All blood pressure measurements should be performed on the same arm, preferably by the same person.

9.5.1.10.3 Adverse Events and Other Events of Interest

An AE is any untoward medical occurrence in a subject who is administered an investigational product. An AE does not necessarily have a causal relationship with the study drug.

The criteria for identifying AEs include the following:

- Any unfavorable and unintended sign (including an abnormal laboratory finding), symptom, or disease temporally associated with the use of an investigational product, whether or not considered related to the investigational product
- Any new disease or exacerbation of an existing disease
- Any deterioration in non-protocol-required measurements of a laboratory value or other clinical test (e.g., electrocardiogram [ECG] or x-ray) that results in symptoms, a change in treatment, or discontinuation of study drug
- Recurrence of an intermittent medical condition (e.g., headache) not present pretreatment (baseline)
- An abnormal laboratory test result should be considered an AE if the identified laboratory abnormality leads to any type of intervention, whether prescribed in the protocol or not, and after repeat confirmatory testing has been conducted

A laboratory result should be considered by the investigator to be an AE if it includes the following:

- Results in an intervention, based on medical evaluation (e.g., potassium supplement for hypokalemia)

- Results in any out of range laboratory value that in the investigator's judgment fulfills the definitions of an AE with regard to the subject's medical profile

All AEs observed during the study will be reported on the CRF. All AEs, regardless of relationship to study drug or procedure, should be collected beginning from the time the subject signs the ICF through the last visit. AEs reported prior to randomization will be termed medical history. SAEs will not be considered medical history and will be collected for 72 hours after the last dose.

Abnormal laboratory values should not be listed as separate AEs if the values are considered to be part of the clinical syndrome that is being reported as an AE. Any laboratory abnormality considered to constitute an AE should be reported as an AE on the CRF.

It is the responsibility of the investigator to review all laboratory findings in all subjects and determine if they constitute an AE. Medical and scientific judgment should be exercised in deciding whether an isolated laboratory abnormality should be classified as an AE.

Every effort must be made by the investigator to categorize each AE according to its severity and its relationship to the study treatment.

Assessing Severity of Adverse Events:

AEs will be graded on a 3-point scale (mild, moderate, severe) and reported in the detail indicated on the CRF. The definitions are as follows:

Mild	Discomfort noticed, but no disruption of normal daily activity
Moderate	Discomfort sufficient to reduce or affect normal daily activity
Severe	Incapacitating, with inability to work or to perform normal daily activity

The criteria for assessing severity are different than those used for seriousness (see Section [9.5.1.10.3](#), Serious Adverse Events and Other Events of Interest for the definition of an SAE).

The causal relationship of the study drug to an AE will be assessed as related or unrelated, as follows:

Assessing Causality of Adverse Events:

Table 3. Assessment of Causality of AEs

Term	Definition
Definitely related	The AE is clearly related to the investigational agent(s) or research intervention: the AE has a temporal relationship to the administration of the investigational agent(s) or research intervention and follows a known pattern of response, and no alternative cause is present.
Probably related	The AE is likely related to the investigational agent(s) or intervention: the AE has a temporal relationship to the administration of the investigational agent(s) or research intervention and follows a known or suspected pattern of response, but an alternative cause may be present.
Possibly related	The AE may be related to the investigational agent(s) or intervention: the AE has a temporal relationship to the administration of the investigational agent(s) or research intervention and follows a suspected pattern of response, but an alternative cause is present.
Unrelated (or Not Related)	The AE is clearly not related to the investigational agent(s) or intervention: the AE has no temporal relationship to the administration of the investigational agent(s) or research intervention, and follows no known or suspected pattern of response, and an alternative cause is present.

AE = adverse event.

